### **5.3 Withdrawal of Patient from the Study**

Patients who withdraw before Cycle 1 Day 42 during the Dose Escalation Phase for a reason unrelated to drug toxicity or efficacy may be considered to have inadequate data to support efficacy assessment (see [Section 4.1.1](#)). In this case, replacement patients may be enrolled but the patients will be considered in intention to treat. These patients will be followed for safety assessments (see [Section 12.2](#)).

See [Section 4.5.1](#) for replacement criteria for those patients who were planned to have paired tumor biopsies.

Procedures for handling patients who fail to appear for study visits and criteria regarding when to consider patients lost-to-follow-up (LTFU) will be defined in the Study Procedures

Manual. A patient may be determined to be LTFU after there have been 3 documented phone contact attempts. If this fails, a certified letter should be sent to the patient. Only after these attempts have failed can a patient be determined to be LTFU.

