2.2 Cohort Expansion Phase

2.2.1 Primary Objective

To investigate antitumor activity of MGD007 combined with MGA012 when dosed at the MTD (or maximum administered dose [MAD] if no MTD is defined) as measured by objective response rate, disease control rate and PFS rate at 16 weeks in patients with relapsed/refractory metastatic colorectal carcinoma using both conventional Response Evaluation Criteria in Solid Tumors (RECIST 1.1) and immune-related response criteria (irRECIST).

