4 ANALYSIS POPULATIONS

4.1 Analysis Populations

The study analyses will be performed on the following populations:

- **Safety Population:** All patients who received at least one dose of any study drug. This population will be used for analyses of safety, PD, and immunogenicity. It will also be used for summary of baseline data and analyses of PFS and OS.
- **Response Evaluable Population:** All patients who received at least one dose of any study drug, had baseline measurable disease, and had at least one post-baseline radiographic tumor assessment or discontinued treatment due to clearly documented, clinically progressive disease or death. This population will be used for summary of tumor assessment data and analyses of response rates.

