6.6 Efficacy Endpoint Analyses

6.6.1 Analyses of Response Endpoints

Number and percent of patients with their best overall response will be summarized. The objective response rate (ORR) per RECIST v1.1 is estimated as the proportion of patients in response evaluable population who achieve BOR of CR or PR. Disease control rate is calculated as the proportion of patients who achieve a CR, PR, or SD. Progression-free survival rate at 16 weeks will be calculated by Kaplan-Meier method described in [Section 6.6.2.1](#), based on response evaluable population and safety population, respectively. The 2-sided 95% exact binomial CI of the response rates will be calculated. The response rates per irRECIST will be estimated similarly. Subgroup analyses of these response rates by KRAS gene type (wild and mutant) and by MMR status (MSS and MSI-H) will be performed.

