6.6.2 Analyses of Time to Event Endpoints

6.6.2.1 PFS and irPFS

The Kaplan-Meier method will be applied to estimate PFS curve, median PFS, and PFS rates at 4 (corresponding to 16 weeks), 6, and 12 months. The method of Brookmeyer and Crowley (1) will be used to construct 95% CI for median PFS. The 95% CIs for PFS rate at 4, 6, and 12 months will be calculated by normal approximation after log(-log) transformation.

For primary PFS analysis, the following table describes the censoring rules.

Table 2 Censoring Rules for Primary PFS Analysis

Situation	Date	Outcome
No baseline tumor assessments	First dose date	Censored
Death prior to first scheduled tumor assessment	Date of death	Progressed
No post-baseline tumor assessments in absence of death prior to first scheduled tumor assessment	First dose date	Censored
Documented progression	Date of progression	Progressed
Initiation of alternative anti-cancer treatments in absence of documented progression	Date of last tumor assessment prior to initiation of such treatment	Censored
Death or documented progression immediately after missing two or more consecutive scheduled tumor assessments	Date of last tumor assessment prior to missed assessments	Censored

PFS will be analyzed by MMR status and by KRAS gene type when sample size warrants. A sensitivity analyses for PFS may be performed to assess the robustness of above primary PFS analysis. For this sensitivity analysis, the censoring rules are the same as in **Table 2** except that the documented progression or death will be considered as an event, regardless of when it occurs during the study.

In addition, above analyses for PFS will also be repeated for irPFS.

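### The Safety Population 16-week PFS rate repeats the Response Evaluable rate by construction, so the plan has no all-treated estimate of this primary expansion measure

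*SAP*

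**What the plan says.** The Cohort Expansion primary objective (SAP 2.2.1, Protocol 3.2.1) assesses antitumor activity "as measured by objective response rate, disease control rate and PFS rate at 16 weeks". SAP 6.6.1 and Protocol 14.6.1 compute the 16-week rate by Kaplan-Meier, "based on response evaluable population and safety population, respectively".

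Under SAP 4.1 the Safety Population is every dosed patient. The Response Evaluable Population also requires measurable disease at baseline and that the patient "had at least one post-baseline radiographic tumor assessment or discontinued treatment due to clearly documented, clinically progressive disease or death".

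Three rows of SAP Table 2 (Protocol Table 14) decide what happens without usable scans:

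- "No baseline tumor assessments": censored at first dose.
- "Death prior to first scheduled tumor assessment": an event on the date of death.
- "No post-baseline tumor assessments in absence of death prior to first scheduled tumor assessment": censored at first dose.

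SAP 5.1.2 makes PFS progression a radiographic finding. SAP 6.6.2.1 allows, but does not require, a sensitivity analysis in which a documented progression or death counts whenever it occurs; the other Table 2 rules stay. The same analyses are repeated for irPFS.

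**The concern.** A second population is useful only if it can give a different answer. The Safety Population row carries a larger N and looks like an all-treated estimate, so a reader may take its agreement with the evaluable-only row as reassurance about early dropout. If the agreement follows from the censoring table, that reassurance is empty. Patients who leave before the first scan (Day 56) for toxicity or withdrawn consent are then without effect on both versions of a primary measure.

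Protocol 5.3 says of escalation patients who withdraw early that "replacement patients may be enrolled but the patients will be considered in intention to treat". The SAP defines no intention-to-treat set; the Safety Population is the nearest to one.

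**Working it through.** **The plan's own figure.** No target or assumed 16-week PFS rate is given. The only related figures are the exact intervals for 2 to 7 responses in 25 (SAP Table 1, Protocol Table 13). Clopper-Pearson limits reproduce all six rows, for example 6/25 = 24%, 9.4 to 45.1.

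**Who is in the Safety Population only?** Measurable disease is inclusion criterion 6. A dosed patient is therefore normally outside the Response Evaluable Population only when there is no post-baseline scan and treatment stopped for something other than clinical progression or death. Table 2 row 3 censors that patient at first dose unless death comes before the first scheduled scan. By the SAP 5.1.2 formula, PFS is then (0 + 1)/(365.25/12) = 0.03 months, or one day.

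**Effect on Kaplan-Meier.** S(t) is the product of (1 - d/n) over event times. The Greenwood sum is the total of d/(n(n - d)), and the log(-log) limits depend only on these two. A patient censored on day 1 is in no n at any later event time, so S, its variance and its limits do not change. Adding 1 to 7 day-1 censorings to 2,000 random data sets changed none of the results.

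**Worked example (assumed data).** There are 25 dosed patients. Five have no scan and are alive at day 56. The other 20 are evaluable: 1 death on day 35, 9 progressions on day 56, 4 on day 112, and 6 progression-free.

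- Response Evaluable: (19/20)(10/19)(6/10) = 30.0%. The Greenwood sum is 1/380 + 9/190 + 4/60 = 0.1167, and the limits are 12.3 to 50.1.
- Safety under Table 2: the risk set on day 35 is again 20, so 30.0% (12.3 to 50.1).
- Safety with the five counted as failures on day 56: (24/25)(10/24)(6/10) = 6/25 = 24.0%. Log(-log) limits are 9.8 to 41.7; exact limits are 9.4 to 45.1.
- Safety with one of the five stopping for an adverse event and dying on day 45: 6/21 = 28.6% (11.7 to 48.2), so here the populations differ.

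**Range over k, which the documents do not give.** With no other censoring before week 16, m progression-free patients give m/(25 - k) under both planned analyses and m/25 among all treated, a ratio of 25/(25 - k). If the k are replaced, so that 25 are evaluable and 25 + k treated, the ratio is (25 + k)/25.

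| k | Progression-free / evaluable (assumed) | Planned rate, both populations | Dropouts counted as failures | 25/(25-k) | (25+k)/25 |
|---|---|---|---|---|---|
| 1 | 7/24 | 29.2% | 28.0% | 1.04 | 1.04 |
| 2 | 6/23 | 26.1% | 24.0% | 1.09 | 1.08 |
| 3 | 7/22 | 31.8% | 28.0% | 1.14 | 1.12 |
| 5 | 6/20 | 30.0% | 24.0% | 1.25 | 1.20 |
| 7 | 5/18 | 27.8% | 20.0% | 1.39 | 1.28 |

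Censoring the dropouts at an assumed last contact on day 28 or 42 moves the rate by at most 0.4 points over k = 1 to 7, so changing the censoring date does not solve this.

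**A related group.** A patient who stops for clinical progression without a scan belongs to the Response Evaluable Population. Because progression must be radiographic, such a patient alive at the first scheduled scan is censored at first dose in both populations.

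**The case against.** Several parts of the case against stand.

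- **Exceptions.** The two results can differ in three ways: a patient who stops for another reason and dies before the first scheduled scan; a patient enrolled without measurable disease who has scans; and, under the optional sensitivity analysis, a later death of an unscanned patient. A reader might infer that no PFS analysis can ever give these patients weight. The sensitivity analysis shows otherwise, although a living unscanned patient still contributes nothing there.
- **Bias.** A reader might infer that the reported rate is too high by 25/(25-k). The documents do not support that. The factor compares the planned rate with a different quantity, in which every dropout is a failure.
- **Frequency.** A reader might carry over the earlier MGD007 study (Protocol Tables 1 and 2), where 75 - 59 = 16 of 75 (21%) were not evaluable. That study was ongoing, and its evaluability definition did not include death. Its weekly groups point in opposite directions: 11 of 11 evaluable at 0.6 and 1 µg/kg, 5 of 10 at 0.8 µg/kg. Diarrhea led to drug withdrawal in 3 of 75 patients, none on weekly dosing.
- **Mitigation.** A scan is due at the End of Treatment Visit unless one is recent, and it would make a dropout evaluable. Protocol 9.11 makes that visit optional. SAP 6.3.1 already tabulates reasons for stopping.
- **Context.** The SAP calls the study primarily observational, sets no PFS threshold, and assigns robustness to the sensitivity analysis rather than to the second population. The shifts of about 1 to 8 points lie well inside an interval of 12.3 to 50.1.

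These points limit the size and certainty of the problem. None makes the second planned estimate informative about unscanned patients who are alive.

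**Conclusion.** The point holds as one of redundancy and a missing estimate. Except in the cases listed, the Safety Population 16-week rate and its interval equal the Response Evaluable ones by construction, and the plan has no all-treated estimate of this primary expansion measure. Patients with unscanned clinical progression who are alive at the first scheduled scan drop out of both.

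The size depends on an unstated number of patients. For 1 to 7 of 25 it is about 1 to 8 percentage points in the illustrations, assuming that every dropout counts as not progression-free and nobody else is censored before week 16. An upward bias of that size is not demonstrated. It is also not true that the objective response rate already counts these dropouts as non-responders: that rate uses the Response Evaluable Population, which excludes them.

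**What to change.** In SAP 6.6.1 and Protocol 14.6.1, keep the Kaplan-Meier rate and add beside it, for PFS and irPFS, a Safety Population proportion with an exact 95% CI:

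- **Numerator:** patients documented alive and progression-free at week 16.
- **Denominator:** all dosed patients whose first dose was early enough for the week-16 scan to fall before the data cut, judged by date and not by outcome.
- **No post-baseline scan:** these patients, including those who stopped for clinical progression, stay in the denominator and count as not progression-free.
- **Censored after a scan but before week 16** (new therapy, missed scan): state in advance how they count.
- **Reporting:** give the number censored at first dose, with reasons, beside both rates.

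The cost is SAP and protocol wording and one extra table row; no new data are needed. The added rate will be equal or lower, and it is conservative for patients who left without progression, so it should be labelled that way.

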6.6.2 Analyses of Time to Event Endpoints

6.6.2.1 PFS and irPFS

The Kaplan-Meier method will be applied to estimate PFS curve, median PFS, and PFS rates at 4 (corresponding to 16 weeks), 6, and 12 months. The method of Brookmeyer and Crowley (1) will be used to construct 95% CI for median PFS. The 95% CIs for PFS rate at 4, 6, and 12 months will be calculated by normal approximation after log(-log) transformation.

For primary PFS analysis, the following table describes the censoring rules.

Table 2 Censoring Rules for Primary PFS Analysis

Situation	Date	Outcome
No baseline tumor assessments	First dose date	Censored
Death prior to first scheduled tumor assessment	Date of death	Progressed
No post-baseline tumor assessments in absence of death prior to first scheduled tumor assessment	First dose date	Censored
Documented progression	Date of progression	Progressed
Initiation of alternative anti-cancer treatments in absence of documented progression	Date of last tumor assessment prior to initiation of such treatment	Censored
Death or documented progression immediately after missing two or more consecutive scheduled tumor assessments	Date of last tumor assessment prior to missed assessments	Censored

PFS will be analyzed by MMR status and by KRAS gene type when sample size warrants. A sensitivity analyses for PFS may be performed to assess the robustness of above primary PFS analysis. For this sensitivity analysis, the censoring rules are the same as in **Table 2** except that the documented progression or death will be considered as an event, regardless of when it occurs during the study.

In addition, above analyses for PFS will also be repeated for irPFS.

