##### **4.4.1 Dose Delays in Escalation and Expansion Cohorts**

Patients who experience toxicity that is potentially dose-limiting should have study drug held pending assessment, management, and resolution of the toxicity. For patients in whom the toxicity is assessed to be unrelated to study drug or for whom the toxicity does not meet the

criteria for DLT, therapy may be re-instituted at the same dose and schedule that was administered prior to the event, presuming the toxicity has resolved as per guidelines outlined in [Section 7](#). Dose interruptions of up to 28 days are allowed. Reinstitution of therapy shall be conducted as follows:

- The procedures at the originally scheduled missed visit should be performed as soon as possible with treatment reinstated as if no delay had occurred, picking up at the day where the interruption occurred, and patients should receive the planned dose and have assessments performed as outlined in the Time and Events Schedule ([Appendix 1](#)).

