### 14.6.3 Time-to-event Endpoints and Analyses

Progression-free survival will be defined as the time from the first dose date of MGD007 to the date of first documented progression or death from any cause, whichever occurs first. The documented progression is determined by objective assessment of disease per RECIST v1.1 and irRECIST, respectively. For patients who are not known to be dead or progressed at the time of data cut-off for PFS analysis, the PFS will be censored at the date of the last tumor assessment. Specifically, the following censoring rules will be applied as primary analysis of PFS. Sensitivity analyses may be performed to assess the robustness of the primary PFS analysis and will be described in the SAP.

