5.1.2 Time to Event Endpoints

- Progression-free survival (PFS): The PFS is defined as the time from the first dose date of MGD007 to the date of first documented progression or death from any cause, whichever occurs first. For patients who are not known to be dead or progressed at the time of data cut-off for PFS analysis, the PFS will be censored at the date of the last tumor assessment. The documented progression is determined by radiographic assessment using RECIST v1.1. PFS will be calculated as:

$$\text{PFS (months)} = (\text{date of event [documented progression or death] or date of censoring} - \text{first dose date} + 1) / (365.25/12)$$

- Immune related PFS (irPFS): The irPFS is defined as the time from the first dose date of MGD007 to the date of first documented immune related progression (irPD) or death from any cause, whichever occurs first. For patients who are not known to be dead or progressed at the time of data cut-off for irPFS analysis, the irPFS will be censored at the date of the last tumor assessment. The documented irPD is determined by radiographic assessment using irRECIST. The irPFS will be calculated as:

$$\text{irPFS (months)} = (\text{date of event [documented immune related progression or death] or date of censoring} - \text{first dose date} + 1) / (365.25/12)$$

- Duration of response (DoR): The DoR is defined as the time from the date of initial response (CR or PR) to the date of first documented progression or death from any cause, whichever occurs first. The DoR is calculated only for the responders. For responders who are not known to be dead or progressed at the time of data cut-off for DoR analysis, the DoR will be censored at the date of the last tumor assessment. The documented progression is determined by radiographic assessment using RECIST v1.1. DoR will be calculated as:

$$\text{DoR (months)} = (\text{date of event [documented progression or death] or date of censoring} - \text{date of initial response} + 1) / (365.25/12)$$

DoR may also be determined by irRECIST.

- Overall survival (OS): The OS is defined as the time from the first dose date of MGD007 to the date of death from any cause. For patients who are not known to be dead at the time of data cut-off for OS analysis, the OS will be censored at the time they are last known to be alive. OS will be calculated as:

$$\text{OS (months)} = (\text{date of death or last known alive} - \text{first dose date} + 1) / (365.25/12)$$

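### The PFS censoring table censors a known death at first dose when the patient missed only the first scheduled scan

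*SAP*

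**What the plan says.** SAP 5.1.2 runs PFS from first dose of MGD007 to "the date of first documented progression or death from any cause, whichever occurs first". The general censoring rule, in the same section and in Protocol 14.6.3, covers a limited group: "For patients who are not known to be dead or progressed at the time of data cut-off for PFS analysis".

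SAP Table 2 and Protocol Table 14 then give identical operational rules. Three of the six rows matter here:

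- **Row 2** makes a death an event at the date of death if it precedes the first scheduled assessment.
- **Row 3** censors at first dose: "No post-baseline tumor assessments in absence of death prior to first scheduled tumor assessment".
- **Row 6** censors at the last assessment before the gap: "Death or documented progression immediately after missing two or more consecutive scheduled tumor assessments".

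SAP 6.6.2.1 adds: "A sensitivity analyses for PFS may be performed to assess the robustness of above primary PFS analysis". In that analysis "documented progression or death will be considered as an event, regardless of when it occurs during the study". The SAP repeats the PFS analyses for irPFS.

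The 16-week PFS rate is one of three measures in the Cohort Expansion primary objective (SAP 2.2.1). It is estimated by Kaplan-Meier "based on response evaluable population and safety population, respectively" (SAP 6.6.1).

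**The concern.** Row 3 exempts only deaths before the first scheduled assessment. A patient with no post-baseline scan who dies after that date, having missed one scan, is left in row 3 and censored at first dose even though the death is known. That departs from the PFS definition, and neither document gives a reason. It also sits badly with row 6, under which a single missed scan followed by death leaves the death as an event.

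Such deaths can become known without a scan. The 8-weekly scans run only during treatment (Protocol 11.1.1), the End of Treatment visit is optional though encouraged (Protocol 9.11), and survival is followed every 3 months (Protocol 11.1.2). Censoring these patients at first dose takes known failures out of the risk set before any event has occurred, so a primary-objective estimate would come out too high.

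**Working it through.** **1. The plan's own figures.** The documents give no figure for the effect of the censoring rule. Their only precision figures for the expansion are the exact 95% intervals for 2 to 7 responses out of 25 (SAP Table 1, Protocol Table 13). Clopper-Pearson limits reproduce all six rows; for 5/25 the interval is 6.8 to 40.7%.

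**2. One patient through the table.** Take a patient with a baseline scan, on treatment, no dose interruption and no new anti-cancer therapy. The Day 56 scan is missed and death is on Day 70, before the second scan at about Day 112.

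- Row 2 does not apply, because the death is after the first scheduled assessment.
- Row 6 does not apply, because only one assessment was missed.
- Row 3 applies, so the patient is censored at first dose.

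With the SAP formula, (date − first dose date + 1)/(365.25/12), PFS is 1/30.4375 = 0.03 months, censored. By the definition it is 70/30.4375 = 2.30 months, an event.

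**3. Comparison patient.** A patient scanned at Day 56 who misses only the Day 112 scan and then dies is not caught by row 6, so the death is an event. The same single miss gets opposite codes.

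**4. Where the case is definite.** The Day 70 result assumes no delay. Protocol 4.4.1 says "Dose interruptions of up to 28 days are allowed", which could move the first scan from Day 56 to about Day 84; a Day 70 death would then be a row 2 event. For a patient who stopped treatment before the first scan fell due, the answer turns on whether that scan still counts as scheduled.

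**5. Effect on the 16-week rate, Safety Population.** Inputs: n = 25 (SAP 3.2, Protocol 14.1); m = number progression-free at 16 weeks (assumed); k = number of such deaths before Day 112 (assumed, since the documents give no basis for it). Apart from the k deaths there is no censoring before Week 16. The plan then gives m/(25 − k); counting the deaths as events gives m/25.

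| m | Deaths counted | Plan, k = 1 | k = 2 | k = 3 |
|---|---|---|---|---|
| 3 | 12.0% | 12.5% | 13.0% | 13.6% |
| 5 | 20.0% | 20.8% | 21.7% | 22.7% |
| 7 | 28.0% | 29.2% | 30.4% | 31.8% |

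For m = 5 the log(-log) 95% intervals are 7.3 to 37.2% with the deaths counted, against 7.6 to 38.5, 7.9 to 39.9 and 8.3 to 41.4% under the plan.

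**6. Response Evaluable Population.** An unscanned patient is in this population only if treatment stopped for documented clinical progression or death (SAP 4.1). If q of the k deaths qualify, n = 25 − k + q. The plan gives m/(25 − k) and the corrected rate is m/(25 − k + q). With m = 5 and k = 3 the plan gives 5/22 = 22.7%. The corrected rate is 22.7, 21.7, 20.8 or 20.0% for q = 0, 1, 2 or 3. There is no bias when none qualifies.

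**The case against.** **The tables are the operational rule.** Protocol 14.6.3 introduces the table as the specific rule for the primary PFS analysis, so it may qualify the definition. That stands as a general point. It does not explain why one missed scan is handled one way for unscanned patients and the other way for scanned ones.

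**The exposed group is narrow.** This largely stands. Patients enter with ECOG 0 or 1 and a life expectancy of at least 12 weeks (Protocol 5.1). The End of Treatment visit includes a CT or MRI unless one was done less than 28 days earlier (Protocol 9.11, Appendix 1), and a patient scanned there leaves row 3. An affected patient must have no post-baseline scan at all, start no new therapy, and die between the first and second scan dates. Nothing in the documents says that k would reach 2 or 3.

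**The sensitivity analysis and OS count these deaths.** They do, but the sensitivity analysis is optional and changes row 6 as well, so it does not isolate this question. Neither analysis alters the primary estimate.

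**Stronger readings that the documents do not support.**

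- A reader might infer that every unscanned death after Day 56 is censored. For patients off treatment that is open. If no scan was due once treatment stopped, row 2 could make the death an event. The derivation of scheduled dates may also sit in the statistical programming plan, which is not among the documents.
- A reader might infer that a death just after Day 112 shows the rule also biasing the rate downward. That depends on the landmark. The SAP reports the rate at 4 months, which is 4 × 365.25/12 = 121.75 days. By then a Day 115 death is a failure. If one of 5 patients otherwise progression-free dies unscanned on Day 115 after one missed scan, the corrected rate is 4/25 = 16.0% against 4/24 = 16.7% under the plan. The bias is again upward.

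**Conclusion.** The point holds on the text of both tables. Row 3, with row 2's cut-off, censors at first dose a patient on treatment when the first scan fell due who missed only that scan, had no later one, and is known to have died. This contradicts the PFS definition and does not match the two-miss threshold in row 6. For patients who stopped treatment before the first scan was due, the outcome is undefined rather than wrong.

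In the Safety Population the bias is upward for such deaths before the 16-week landmark: 0.8, 1.7 or 2.7 percentage points at 5 of 25 progression-free with k = 1, 2 or 3. These sizes rest on assumed m and k and on no other censoring before Week 16. The Response Evaluable rate is affected only through unscanned patients who qualify by discontinuing for clinical progression or death. Every shift is small beside the plan's own 6.8 to 40.7% interval for 5/25. The SAP calls its summaries mainly descriptive and sets no PFS threshold, so what is at stake is the accuracy and consistency of a reported estimate. It is worth correcting because the rate belongs to a primary objective and the correction is cheap.

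**What to change.** In SAP Table 2 and Protocol Table 14:

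1. **Row 2.** A death with no post-baseline assessment is an event at the date of death, unless two or more consecutive scheduled assessments were missed before it.
2. **Row 3.** Limit it to patients with no post-baseline assessment who are not known to have died. State that unscanned deaths after two or more missed assessments are censored at first dose under row 6, and that row 5 takes precedence if alternative anti-cancer treatment started first.
3. **One definition of a scheduled assessment** for rows 2, 3 and 6, based on the assessments that the protocol schedules for that patient. Notional scans after treatment has stopped should not count as missed, because the protocol does not schedule 8-weekly scans then.
4. **Sensitivity analysis.** Commit to performing it, for both PFS and irPFS, with its definition unchanged.

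The cost is edits to two rows and a definition in each table, one word in the SAP for the sensitivity analysis, and a small programming specification for each patient's scheduled assessments. No new data are needed. The reported Safety Population rate may be slightly less favourable.
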